5.0 Inclusion and Exclusion Criteria/ Study Population

Only women 18-45 years who are lactating and their preterm infants (<35 weeks) within the first week postpartum will be eligible for the study. Men will be excluded on the basis of the study criterion of lactation. Infants of both genders will be followed along with their mothers. Women who deliver at MUSC will be eligible for participation.

- a. **Inclusion Criteria for Lactating Women:** Women with documentation of fully breastfeeding who present within one month of delivery, who are 18-45 years old and in good general health will be eligible for participation.
- b. **Exclusion Criteria for Lactating Women:** Women with preexisting type I or type II diabetes, hypertension requiring medication or parathyroid disease will not be eligible for participation in the study. Those women with active thyroid disease will not be eligible for inclusion in the study; however, women who have normal thyroid parameters on thyroid replacement hormone will be eligible for participation in the study. In addition, because of

the potentially confounding effect of multiple gestations/births (e.g. twins, triplets), women with multiple gestations/births will not be eligible for participation in the study.

No racial or ethnic groups will be excluded from this study.

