6. Laboratory Data from Blood and Urine Samples: At initiation of the study and at each monthly visit (1, 2, and 3), each woman will have blood sample drawn (20 mL) for detailed analysis of vitamin D and calcium homeostasis. The total blood to be drawn from woman during the 3-month study period will be 60mL (<1/2 cup). In addition, she will be asked to provide a urine sample to measure her urinary calcium/creatinine. A total of up to 4 blood and urine samples will be obtained from each mother, depending on continued participation in the study.

7. Milk Samples: At time of initiation of the study and at each monthly visit (1, 2, and 3), each mother will provide a milk sample from her left breast. The skin will be washed with warm water prior to pumping. The amount obtained will be less than 20 mL at each visit. This milk can be pumped that day and kept refrigerated or pumped at time of visit. This will then be run on the Calais Milk Analyzer to be tested for Fat, Total Protein, True Protein, Lactose, and Calorie/ounce.

8. Degree of Skin Pigmentation will be measured at each visit using the Smart Probe 400, a commercially available spectrometer, which is placed lightly on the skin. Sites to be measured include the inner and outer lower arm and the buttocks.

9. Depression/Anxiety Screening: Each mother enrolled in the study will complete the Edinburgh Postnatal Depression Scale (EPDS) at each monthly study visit. Women who score above the threshold consistent with possible depression will be referred to the appropriate trained professional. Any woman who responds “yes” to the suicide related statements in the EPDS will be immediately referred to the Emergency Room for further evaluation and treatment.

Infant

1. Outpatient Visits: Each mother will be asked to bring her infant as a scheduled outpatient at her monthly visits. If still admitted to the NICU, these monthly visits will be held in the MUSC NICU. If discharged, visits will be held at Infant High-Risk Clinic or NEXUS clinic. These visits will be the initial at approximately 3-7 days of life, then at months 1, 2, and 3.

2. Questionnaires: We will ask each mother to complete a questionnaire about her baby’s dietary type (breastfeeding, formula-supplementation), and feeding frequency for the week prior to each outpatient visit. Each questionnaire will take approximately 5 minutes to complete. See maternal section table.

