3. Daily Vitamin D Supplementation: Infants of mothers who receive 600 IU of vitamin D₃ will receive 400 IU of vitamin D₃ in the form of drops. Infants of mothers who receive 6600 IU of vitamin D₃ will receive placebo drops.

3. General Health Assessment of Infant: At 1 week after delivery and then monthly until 3-months of age, each enrolled infant will undergo a growth (measuring head circumference, weight, length, head circumference, Ponderal index, body mass index [BMI]) and general health assessment.

4. PEAPOD Assessment: Prior to discharge from the NICU, the infant will also be placed in the PEAPOD® for body mass composition analysis. The material and data will be specifically obtained for research purposes. There is minimal risk. This is a safe device in which the infant lays in for 2 minutes.

5. Blood Sample from Infant: At initial visit, 1-, 2- and 3-months of age, each infant will have a blood sample 4mL (<1tsp) taken from either a vein (infant’s hand, arm or foot) or the heel. Total amount obtained will be less than 12mL (<1 1/2 tablespoon). The serum sample will be analyzed for vitamin D and calcium concentration. Parents will be counseled that if their infant is vitamin D deficient, the infant’s primary care physician and they will be contacted regarding the finding(s) with recommended follow-up.

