- b. **Infant:** The total amount of blood to be drawn during the study period (initial visit and months 1, 2, and 3) will be 2 mL at each visit (less than a teaspoon or less than 0.6% of the infant's total blood volume) or 10 mL (<2 tablespoons) over the course of 3 months. Using aseptic technique, blood will be drawn from the infant's hand, arm or heel either via venipuncture or heel stick. As with any blood draw, there may be a slight pain when the needle is inserted into a vein. Momentary discomfort may occur when skilled technicians or nurses perform phlebotomy. Pressure will be applied to the arm following the procedure to minimize the risk of bruising; however, despite these efforts, a bruise may form at the site. Lastly, there is a slight chance of inflammation of the vein and/or blood clot formation, but this is extremely rare.

2. The Risks of Randomization in the Study:

- a. There is a possibility that the treatment that each subject receives may prove to be less effective or to have more side effects than the other study treatment(s) or other available treatments. Because the ideal dose of vitamin D during lactation for mothers of preterm infants is unknown presently, the only way to determine the optimal dose is through a well-controlled, well designed scientific study that we are attempting to initiate.

3. The Risks of High Dose Maternal Vitamin D Supplementation are hypercalciuria and hypercalcemia.

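### The infant blood draw is 4 mL per visit in Section 10 but 2 mL in Section 15 for the same four visits, and Section 10's four draws make 16 mL against a stated total below 12 mL

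*Protocol*

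**What the plan says.** Section 10.0 (Infant, item 1) sets four infant visits: "These visits will be the initial at approximately 3-7 days of life, then at months 1, 2, and 3". Item 5 of the same list specifies the draw at each of them: "each infant will have a blood sample 4mL (<1tsp) taken from either a vein", or alternatively from the heel. It then gives the study total: "Total amount obtained will be less than 12mL". The stated purpose is: "The serum sample will be analyzed for vitamin D and calcium concentration".

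Section 15 (Risks to Subjects, item 1b) covers the same time points, "initial visit and months 1, 2, and 3", but gives the volume as "2 mL at each visit (less than a teaspoon or less than 0.6% of the" infant's blood volume, "or 10 mL (<2 tablespoons) over the course of 3 months".

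Section 5.0 defines the population: mothers and "their preterm infants (<35 weeks) within the first week postpartum will be eligible".

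The maternal volumes are also stated twice. Section 10.0 (Mother, item 6) gives 20 mL per visit, up to four samples and a total of 60 mL. Section 15 (item 1a) gives 15 mL per visit, at most four draws and a total of no more than 60 mL.

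**The concern.** Section 10 is the procedure that staff carry out, and Section 15 is the basis on which the burden and risk of blood sampling are judged. They describe the same draws on the same infants with volumes that differ by a factor of two. Section 10's total also cannot be reached from its own volume and schedule.

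Anyone weighing infant risk from Section 15 sees half of the per-visit volume that Section 10 orders. The participants are preterm, and the first draw falls at about 3–7 days of life, when blood volume is smallest. What is at stake is participant burden and the accuracy of the risk statement, not the trial's power or its estimand.

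**Working it through.** **Inputs, all from the protocol.** Infant draws: 4 (initial visit and months 1, 2 and 3; Sections 10 and 15). Infant volume per draw: 4 mL (Section 10) or 2 mL (Section 15). Stated infant totals: below 12 mL (Section 10) and 10 mL (Section 15). Maternal volume per draw: 20 mL (Section 10) or 15 mL (Section 15), with a stated total of 60 mL in both.

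**Formula.** Total = volume per draw × number of draws.

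| Source | Calculation | Result | Stated total | Draws that would give the stated total |
|---|---|---|---|---|
| Infant, Section 10 | 4 × 4 | 16 mL | below 12 mL | 3 gives exactly 12 mL, still not below 12 |
| Infant, Section 15 | 2 × 4 | 8 mL | 10 mL | 5 |
| Mother, Section 10 | 20 × 4 | 80 mL | 60 mL | 3 |
| Mother, Section 15 | 15 × 4 | 60 mL | at most 60 mL | 4 (consistent) |

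Section 10's infant total is not reproduced by its own inputs, nor is Section 15's.

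**Size of the excess at 4 mL.** 16/12 = 1.33, so at least 33% over Section 10's total. 16/10 = 1.60, so 60% over Section 15's total. The running volume is 4, 8, 12 and 16 mL. The third draw already passes 10 mL and is no longer below 12 mL.

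**What the totals allow.** Over four draws, a total below 12 mL needs less than 12/4 = 3 mL per draw. A total of 10 mL needs 10/4 = 2.5 mL per draw. A 4 mL draw is compatible with neither. A 2 mL draw stays under both, though 8 mL does not reproduce the 10 mL.

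**Mother.** 80/60 = 1.33, so 33% over the stated total.

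**Secondary check: the 0.6% share in Section 15.** For 2 mL to be under 0.6%, blood volume must exceed 2/0.006 = 333 mL; for 4 mL, 4/0.006 = 667 mL. Converting to weight needs an assumption that is not in the protocol: 80–100 mL of blood per kg.

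- 2 mL is below 0.6% only above 333/100 = 3.3 kg to 333/80 = 4.2 kg.
- 4 mL is below 0.6% only above 667/100 = 6.7 kg to 667/80 = 8.3 kg.

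| Illustrative weight | 2 mL as share of blood volume | 4 mL as share of blood volume |
|---|---|---|
| 1 kg | 2.0–2.5% | 4.0–5.0% |
| 2 kg | 1.0–1.25% | 2.0–2.5% |

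**The case against.** The strongest reply is that this is a clerical slip with no statistical consequence. No endpoint, sample size or analysis depends on it, the totals are not stopping rules, and nothing shows that a month-3 sample would be lost. That is correct and limits the severity. It does not remove a two-fold conflict in an operative instruction for preterm infants.

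Other replies have partial force:

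- **Understatement.** Section 15 describes half of the volume per visit only. On totals it states 10 mL against 16 mL, which is 10/16 = 62.5%.
- **Baseline draw left out.** This could explain totals that match three draws, but the text does not say so, and three infant draws still give 12 mL, not less.
- **Choice of 2 mL.** The protocol does not show that 2 mL was intended. Staying under both totals makes it a reasonable default, not a proven correction.
- **Maternal volumes.** Both maternal totals are 60 mL, so the 20 mL figure is the likelier error there. Because Section 10 allows up to four samples, 80 mL is a maximum.
- **The 0.6% share.** The conversion to weight rests on assumed blood volume per kg and illustrative weights, so it should not carry the point.
- **Household measures.** One and a half tablespoons is about 22 mL, so that gloss fits 12 or 16 mL and settles nothing.

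**Conclusion.** The concern holds and should be fixed. The infant volume is 4 mL in Section 10 and 2 mL in Section 15 for the same four visits. Section 10's schedule yields 16 mL, at least 33% above its own ceiling and 60% above Section 15's total. Section 15's total does not match its schedule either (8 mL against 10 mL). Section 10's maternal figures are also inconsistent (80 mL against 60 mL), while Section 15's agree. These results are arithmetic on the protocol's own numbers and need no outside assumption.

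The text does not establish which infant figure is the mistake. As a secondary point, under 80–100 mL/kg the 0.6% share is unlikely to hold at the first draw even for 2 mL. Whether families were told 2 mL or 4 mL cannot be judged, because the consent text was not available.

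**What to change.** State one infant per-visit volume and one matching four-draw total, identically in Sections 10 and 15.

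- **Infant default: 2 mL and 8 mL.** First confirm with the laboratory that 2 mL is enough for 25(OH)D and calcium. Also confirm that it covers any infant share of the genetic testing in Section 11.0 and the archived samples in Aim 2; neither passage says whether infant blood is included.
- **If 2 mL is not enough:** keep the larger volume and correct the totals and risk text upward. For 4 mL that means 16 mL in both sections.
- **Mother:** set Section 10 to 15 mL per visit (60 mL over four draws) if that volume suffices; otherwise state 20 mL and 80 mL in both sections.
- **Risk wording:** replace the 0.6% share with mL/kg, or with a percentage at realistic first-draw weights.
- **Consent:** check that the consent text gives the same volumes.

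The cost is a text correction in two sections plus a check of assay volumes and consent wording. If the smaller volumes suffice, design, sample size and analysis stay as they are. If not, the stated burden rises to as much as 16 mL (infant) and 80 mL (mother), or the assay list must be cut. The restated blood-volume share at the first draw will probably look less favourable in either case.

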11.0 Specimen Collection and Banking

Blood, urine and milk specimens will be collected. The specimen will be marked with patient name, subject ID, date and time of collection as well as MRN. This is necessary to ensure integrity of the data is maintained. These specimens will be stored in a double

locked laboratory maintained by [name] and [name] in the Darby Children's Research Institute (DCRI), Room 304. The specimens will be stored for up to 5 years. The PI and the co-investigators as listed on the IRB application will have access to the specimens and associated data and will be responsible for receipt or transmission of them. Specimens will not be sent to an outside facility.

Specimen/Banking for Future Use

- Describe the linkages to subjects and who will have access to subject identities.
 - Specimens will be stored in -80°C freezer with study ID and participant name, MRN on samples. The samples will be located in the double locked lab of Drs. [name] and [name]. These samples will be destroyed after 5 years.
 - This information will be maintained in a database and all other data, including results of the study will be in a separate database that is password protected with the results by subject ID.
- List the data to be stored or associated with each specimen.
 - In one password-protected database: subject ID, participant name, MRN
 - In a separate password-protected database: subject ID, results
- State whether samples could be used for genetic analysis.
 - Yes, blood samples will be used for genetic polymorphisms of vitamin D binding proteins as this can affect vitamin D metabolism and processing and well as overall vitamin D status.
- Can specimens be withdrawn? If so, what is the process.
 - Yes, if a mother wants her samples withdrawn, she will inform the PI in writing of her request and sample(s) will be destroyed. This will be documented in the database and in the participant research record.

[figure not shown]
12.0 Data Management

All maternal and infant blood and urine samples obtained will be labeled with the patient's name, subject ID number, and medical record number to ensure proper tracking. Each study subject and her infant then will be assigned a specific study number without any reference to the woman or infant's name, which will be used to enter all data into RedCap. We will follow all HIPAA guidelines to maintain protection of patient/subject information. With these precautions in place, there is a remote risk that the samples and data could be linked to the woman and her infant; however, the study number and the name will be kept in a separate file in the locked office of [name]. The data will be entered into a secured database with only the study number entered, thus ensuring that the number and data will be kept separately from the woman and infant's names.

- *Describe the data analysis plan, including any statistical procedures.*

Power Analysis

Treatment Group	V1 [p= 0.03]	V4 [p<0.001]	V1 SD	V4 SD	n	Cohen's D	f
400 IU Vit D/day Mother & Infant Placebo Group	86.5	80.2	31.42	28.19	74	1.668	0.834
6400 IU Vit D/day Mother & Infant Group	98.6	149	35.31	45.88	74		

F tests - ANOVA: Repeated measures, within-between interaction based on effect size calculated from figure above.

Analysis: *A priori*: Compute required sample size

Input: Effect size $f = 0.834$

α err prob = 0.05

Power (1- β err prob) = 0.80

Number of groups = 2

Number of measurements

Corr among rep measures = 0.5

Nonsphericity correction $\varepsilon = 1$

Noncentrality parameter $\lambda = 2$

Critical F = 4.4589701

Output: Noncentrality parameter $\lambda = 25.0400160$

Critical F = 4.4589701

Numerator df = 2.0000000

Denominator df = 8.0000000

Total sample size = 6 (3 per gr)

Actual power = 0.9620629

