1.0 Objectives / Specific Aims

The overall goal of this study is to assess maternal vitamin D status along with diet, and milk composition to, in turn, evaluate if infant vitamin D status can be improved with increased maternal supplementation and diet education. Our **central hypothesis** is that by maximizing maternal vitamin D status, there will be an increase infant 25(OH)D concentration in breastfed, preterm infants. This hypothesis will be tested by performing the following Specific Aims.

Aim 1: Determine the efficacy, effectiveness, and safety of maternal and premature infant vitamin D supplementation as a function of maternal vitamin D status, lactation status, and ethnicity.

H₁: Maternal supplementation of high dose (6,600 IU) vitamin D₃/day will be safe for lactating mothers.

H₂: It is anticipated that only high dose (6,600 IU) vitamin D₃/day supplementation of lactating mothers will provide sufficient antirachitic activity in breast milk to prevent vitamin D deficiency in nursing premature infants, regardless of ethnicity/race.

H₃: High-dose maternal supplementation will be safe and more effective than infant vitamin D supplementation alone, without any adverse side effects or health consequences in the mother or infant.

Consented lactating women who delivered preterm infants <35 weeks' gestation admitted to the MUSC NICU will be randomized 3-7 days following delivery to either 1 of 2 study groups: Group A (standard therapy of 600 IU vitamin D₃/day), Group B (high dose supplementation of 6,600 IU Vitamin D₃/day). As such, infants whose lactating mothers are randomized to the 600-IU/day group will receive 400-IU/day oral vitamin D₃ (recommended practice). Those infants of lactating mothers assigned to Group B will receive placebo. Calcium homeostasis will be monitored in all groups. Safety will be assessed throughout the study on a case-rather than a treatment arm basis using cautionary levels as the stop rule with intervention prior to exceeding normal urinary calcium/creatinine ratios in mothers and serum calcium concentrations in both mothers and infants. Through these proposed studies, the prevalence of vitamin D deficiency among mothers and their infants, and the utility of maternal therapeutic intervention with vitamin D₃ will be assessed.

Aim 2: Aim 2: Evaluate and maximize maternal milk composition.

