4.0 Study Endpoints

- Primary outcomes will be:
 - Infant total circulating 25(OH)D concentration at 3 months
 - Mother total circulating 25(OH)D concentration at 3 months
- Primary or secondary safety endpoints
 - Maternal serum calcium concentration initially and at months 1-, 2-, and 3
 - Maternal urine calcium/creatinine ratios initially and at months 1-, 2-, and 3
 - Infant serum calcium concentration at time points initially and at months 1-, 2-, and 3

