6.0 Number of Subjects

For this initial Pilot study, we will enroll 50 mothers/infant dyads in total, 25 in the control and 25 in the placebo group.

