hypercalciuria and hypercalcemia. There is a small risk that the woman's blood calcium level would increase in response to higher dose vitamin D supplementation. The body responds by excreting calcium in the urine to maintain normal calcium levels. If calcium levels in the blood continue to rise, then serum calcium will increase leading to hypercalcemia. This process takes weeks to months to occur. It takes approximately 3 months to reach steady state on an increased vitamin D intake/regimen. In related studies conducted at MUSC comparing maternal vitamin D supplementation with 400, 2400, or 6400 IU of vitamin D₃/day and their infants for 7 months, there were no differences in infant or maternal safety parameters (22). There were no reported episodes of either hypercalciuria or hypercalcemia in any of the treatment groups. In fact, maternal 25 (OH)D levels were higher in the 6400 IU/day treatment group compared to the 400 IU group. In breastfed infants, there was no statistical difference in the average circulating 25 (OH)D in either treatment arm (22).

- a. To ensure that each lactating mother and her breastfeeding infant and each nonlactating mother (and her formula-feeding infant as a control) maintain normal vitamin D status throughout the study period and not develop hypervitaminosis D, both mother and infant will be screened monthly for hypercalciuria, the first indicator of hypervitaminosis D. All study subjects will be monitored closely for hypervitaminosis D. Operationally, we define caution limits as urinary Ca/creatinine ratio > 0.8 mmol/mmol. Whenever any patient

exceeds the caution limit, a specific case study will be initiated by the Data Safety and Monitoring Committee (DSMC) to examine the contribution of sunlight exposure and other confounding factors. Operationally, we define upper limits as a urinary calcium/creatinine ratio > 1.0 mmol/mmol Ca/creatinine ratio. This is a conservative upper limit as circulating levels achieved in individuals living in sun-rich environments achieve this amount without causing toxicity. The DSMC will be convened to review any patient who exceeds any predefined toxic limit for any outcome. If the elevated levels are unexplained, the patient will be withdrawn from supplementation but will continue to be monitored.

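### The power calculation enters d/2 = 0.834 as a repeated-measures interaction f, so its N = 6 and power 0.962 are wrong for the test it names; the planned 50 dyads are not affected

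*Protocol*

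**What the plan says.** The Power Analysis in Section 12.0 tabulates 25(OH)D in two arms of an earlier trial, 74 per arm.

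- Low-dose row: mean 86.5 at V1 and 80.2 at V4; SDs 31.42 and 28.19.
- 6400 IU row: mean 98.6 at V1 and 149 at V4; SDs 35.31 and 45.88.
- Effect size: Cohen's d = 1.668 and f = 0.834.

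The test is given as "F tests - ANOVA: Repeated measures, within-between interaction based on effect size calculated from figure above". Inputs are f = 0.834, alpha 0.05, target power 0.80, two groups, correlation 0.5 and nonsphericity correction 1. Outputs are lambda 25.040, critical F 4.459, df 2 and 8, power 0.962, and "Total sample size = 6 (3 per gr").

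Section 6.0 sets the size separately, calls the study a pilot and does not refer to the calculation: "we will enroll 50 mothers/infant dyads in total". Section 10.0 plans four samplings: "At initiation of the study and at each monthly visit (1, 2, and 3), each woman will have blood sample drawn", with infants sampled on the same schedule. Section 4.0 has two primary outcomes, the maternal 3-month concentration and "Infant total circulating 25(OH)D concentration at 3 months".

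**The concern.** Halving a Cohen's d gives Cohen's f for two independent groups compared on one measurement. The f of a within-between interaction is a different quantity: the SD of the interaction effects across the group-by-visit cells, divided by the within-cell SD. For two groups at two visits it is the difference in change divided by four SDs, not two, and with a given V1-to-V4 contrast it is smaller still when more visits are included. Entering d/2 in the interaction routine therefore overstates the effect, and the routine then multiplies by the repeated-measures gain.

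At stake is the only statistical justification of size in the protocol. As printed, it tells the reader that three dyads per arm give 96% power. It also leaves unclear what 25 per arm can show for infant 25(OH)D, the subject of the central hypothesis in Section 1.0.

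**Working it through.** **1. Reproduce the printed run.** With k = 2 groups, m measurements and correlation rho:

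lambda = f² × N × m / (1 − rho); df1 = (k − 1)(m − 1); df2 = (N − k)(m − 1).

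The printed df of 2 and 8 at N = 6 require m = 3. Then lambda = 0.834² × 6 × 3 / 0.5 = 25.040, critical F = 4.459, power = 0.9621. All match, so the software arithmetic is right for the f entered. The match also fixes the definition of f in use: the gain m/(1 − rho) = 3/0.5 = 6 is applied to an f that is simply 1.668/2.

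**2. Check that the table was read correctly.** V1 difference: 98.6 − 86.5 = 12.1. Standard error: √[(31.42² + 35.31²)/74] = 5.49. So t = 2.20 and p = 0.029, in line with the printed 0.03.

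**3. Interaction f from the table.**

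- Difference in change: (149 − 98.6) − (80.2 − 86.5) = 50.4 + 6.3 = 56.7.
- Pooled SD: √[(31.42² + 35.31² + 28.19² + 45.88²)/4] = √(5133.66/4) = 35.82.
- Two visits: f = 56.7/(4 × 35.82) = 0.396.
- More visits: f = (56.7/2) × SD(w)/35.82, where w is the fraction of the contrast reached at each visit and SD(w) is its population SD. The path between V1 and V4 is not given, so two assumed paths are shown: linear, and plateau (full contrast from the second visit).

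**4. Power at N = 6 and total N for 80% power, rho = 0.5.**

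| Visits and path | SD(w) | f | lambda at N = 6 | Power at N = 6 | N for 80% |
|---|---|---|---|---|---|
| 2 | 0.500 | 0.396 | 3.76 | 0.320 | 16 |
| 3, linear | 0.408 | 0.323 | 3.76 | 0.282 | 18 |
| 3, plateau | 0.471 | 0.373 | 5.01 | 0.363 | 14 |
| 4, linear | 0.373 | 0.295 | 4.17 | 0.279 | 18 |
| 4, plateau | 0.433 | 0.343 | 5.64 | 0.368 | 14 |

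Holding f = 0.396 fixed at three measurements gives power 0.403 at N = 6 and needs 12. With assumed correlations of 0.3 to 0.7, power at N = 6 over the five rows runs from 0.21 to 0.58.

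**5. Take 1.668 at face value instead.**

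- As a two-group d: a two-sample t-test at 3 per arm has power 0.348; 7 per arm gives 0.817.
- As a difference in change divided by the within-visit SD: f = 1.668/4 = 0.417; at two visits power is 0.348 at N = 6, and 14 in total are needed.

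**6. The planned size.** At N = 50 the lowest power over the five rows is 0.9993; at N = 40 it is 0.995.

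**7. What 25 per arm can show on a single 3-month comparison** (two-sample t, two-sided 0.05, in SD units because no SD labelled as infant is given).

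- 25 evaluable per arm: detectable difference 0.81 SD at 80% power; 95% CI half-width 2.011 × √(2/25) = 0.57 SD.
- 20 per arm, an assumed loss: 0.91 SD and 2.024 × √(2/20) = 0.64 SD.

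**The case against.** **Nothing in the trial uses N = 6.** This stands. Section 6.0 fixes 50 dyads for a pilot without citing the calculation, and 50 exceed every corrected requirement. A reader might infer that the trial is underpowered or should enrol more; the figures show the opposite for the table's effect.

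**The origin of 1.668 may be documented.** A reader might infer that it has no source, because simple ratios from the table miss it: 68.8/38.08 = 1.807 (V4 difference over V4 SDs), and 56.7 over the V1, four-cell and V4 SDs gives 1.697, 1.583 and 1.489. The documents do not support that inference. The text cites a figure that is not reproduced in the copy reviewed, and a change score divided by its own SD reaches about 1.668 at a V1–V4 correlation near 0.56. That origin would not rescue N = 6: an effect standardised by the SD of change already contains the gain from the correlation, and the printed lambda would count it a second time.

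**The infant point is weaker than the arithmetic.** The row label "400 IU Vit D/day Mother & Infant Placebo Group" invites the reading that low-dose infants in the source trial received placebo, whereas here "infants whose lactating mothers are randomized to the 600-IU/day group will receive 400-IU/day oral vitamin". A reader might conclude that the table cannot size this trial's infant contrast. But the other row also joins mother and infant, so the word placebo may describe the group rather than the infant, and the label cannot carry that conclusion. Nor does the text say whose 25(OH)D is shown. The V4 p-value below 0.001, set against the statement in Section 15, item 3, that "In breastfed infants, there was no statistical difference in the average circulating 25 (OH)D in either treatment arm", makes maternal likely but not certain. Hence it is only conditionally true that the infant outcome has no planning figure here.

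**Three measurements against four planned visits** is a minor mismatch, and the input line for that value is blank in the text as read.

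**Conclusion.** The error is real and confined to the power block. The f entered is 2.1 times the two-visit value from the table (0.834/0.396) and 2.2 to 2.6 times the three-measurement value (0.834/0.373 to 0.834/0.323). For the test named, six subjects have power of about 0.28 to 0.37, or 0.40 with f = 0.396 held fixed at three measurements, against 0.962 as printed. The total for 80% power is about 14 to 18, or 12 in that fixed-f case.

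This rests on the table's means and SDs, the protocol's correlation of 0.5, sphericity, and an assumed linear or plateau path between visits. That N = 6 falls short of 80% does not depend on the path, nor on any correlation from 0.3 to 0.7. The adequacy of 25 per arm for the table's effect is not in question. The point should be fixed, because a stated sample size and power are wrong as written, but it does not alter the design.

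**What to change.** Delete the N = 6 / 0.962 block, or rerun it with an interaction f derived from the table and the planned number of visits. Say how d was obtained and which participants' 25(OH)D the table shows. Then restate power for the planned size, for example: Twenty-five dyads per arm give power above 0.99 for the difference in the table.

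If the table is confirmed as maternal, add: For infant 25(OH)D at 3 months, 25 evaluable infants per arm can detect a difference of 0.81 SD with 80% power (two-sided 0.05; 95% CI half-width 0.57 SD), or 0.91 SD (0.64 SD) if 20 per arm are evaluable. The 20 is an illustrative assumption and should be labelled so.

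The cost is one recalculation and a change of wording. No subjects, visits or samples are added. The price is a less favourable stated figure.
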